### 7.1.3 General Appearance

- OC-01 (varenicline) /Placebo Nasal Spray will be formulated at the desired concentration in sodium phosphate buffers and sodium chloride as an aqueous solution, and presented in a multi-use preservative-free nasal pump.
- The product is preservative-free and intended for intranasal use only. The product should not be used if cloudy or if particulate matter is present.
- OC-01 (varenicline) solution must be administered without dilution.

## 7.2 **Other Study Supplies**

For all other study supplies refer to the Non-IP supplies list.

## 8 **STUDY METHODS AND PROCEDURES**

### 8.1 **Participant Entry Procedures**

#### 8.1.1 Overview

Participants as defined by the criteria in [Sections 5.2, 5.3, and 5.4](#) will be considered for entry into this study.

#### 8.1.2 Informed Consent

Prior to a participant's enrollment in the trial (i.e., prior to any study-related procedures), the study will be discussed with each potential participant and participants wishing to participate must be administered and provide written informed consent using an Institutional Review Board (IRB)-approved informed consent form (ICF). The ICF must be the most recent version that has received approval by a properly constituted IRB.

OC-01 (varenicline) Nasal Spray  
Clinical Trial Protocol # OPP-101  
Amendment #1

Sponsor: Oyster Point Pharma, Inc.

### 8.1.3 Washout Intervals

Prohibited medications, treatments, and activities are outlined in the Exclusion Criteria (Section 5.4).

### 8.1.4 Procedures for Final Study Entry

Subjects must meet all inclusion criteria and none of the exclusion criteria.

### 8.1.5 Methods for Assignment to Treatment Groups

Each subject who enters the screening period for the study (defined as the point at which the subject signs the informed consent form (ICF) receives a unique subject identification number before any study-related activities/procedures are performed. This number will be used to identify the subject throughout the clinical study and must be used on all study documentation related to that subject.

The subject identification number must remain constant throughout the entire clinical study.

Subjects who meet the eligibility requirements will be randomly assigned to 1 of 3 treatment groups.

The randomization will be stratified by three factors:

- Pre-procedure (Baseline) anesthetized Schirmer's score ( $\leq 5$ ,  $>5$ ) measured the screening/randomization visit
- Pre-procedure (Baseline) EDS ( $<60$ ,  $\geq 60$ ) measured at the screening/randomization visit
- Study site

A central randomization list will be created using block randomization. Sites will be assigned entire blocks as needed.

## **8.2 Concomitant Therapies**

The use of any concurrent medication, prescription or over-the-counter, is to be recorded on the subject's source document and corresponding eCRF along with the reason the medication was taken.

Concurrent enrollment in another investigational drug or device study during the treatment period is not permitted.

### 8.2.1 Prohibited Medications/Treatments

Disallowed medications/treatments during the study are outlined in the Exclusion Criteria below:

OC-01 (varenicline) Nasal Spray  
Clinical Trial Protocol # OPP-101  
Amendment #1

Sponsor: Oyster Point Pharma, Inc.

- No concomitant use of a nicotinic acetylcholine receptor agonist [Nicoderm®, Nicorette®, Nicotrol NS® (nicotine), Tabex®, Desmoxan® (cytisine), and Chantix® (varenicline)] during the treatment period (Baseline to Day 28) of the study.
- No concomitant use of Restasis® or Xiidra® during the treatment period (Baseline to Day 28) of the study.

### 8.2.2 Escape Medications

No escape medication is required for this study.

### 8.2.3 Special Diet or Activities

No special diets or activity is required for this study.

## 8.3 Examination Procedures

### 8.3.1 Procedures to be Performed at Each Study Visit with Regard to Study Objectives(s)

The following procedures will be performed (see [Appendix 2](#) for description).

#### **Screening/Visit 1 (Day 1): Screening and Randomization**

- Informed consent/Health Information Portability and Accountability Act (HIPAA) consent
- Demographic data, medical history, prior medication (s), and ocular history
- Eligibility Criteria
- Urine pregnancy test (if applicable)
- OSDI® questionnaire
- Eye Dryness Scale (EDS) (visual analog scale) (pre-treatment)
- [REDACTED] Ocular Discomfort Scale (pre-treatment)
- BCVA (pre-and post-treatment procedures)
- Slit lamp biomicroscopy (pre-and post-treatment procedures)
- Corneal fluorescein staining
- Baseline Schirmer's Test
- Schirmer's Test with nasal stimulation (cotton swab)
- Intranasal examination (pre-and post-treatment procedures)
- Randomization
- Dispense study drug/placebo
- Schirmer's Test (concurrent with treatment)
- Administration of study drug/placebo concurrently with Schirmer's Test
- Concomitant Medications
- AE Query

 Procedure will occur after corneal fluorescein staining

 Schirmer's test with nasal stimulation will occur  $\geq 10$  minutes after the Baseline Schirmer's test

OC-01 (varenicline) Nasal Spray  
Clinical Trial Protocol # OPP-101  
Amendment #1

Sponsor: Oyster Point Pharma, Inc.

### **Visit 2 (Day 7 ±2): Dosing Compliance Assessment**

- BCVA
- EDS (visual analog scale)
- Slit lamp biomicroscopy
- Intranasal exam
- Concomitant Medications
- AE Query

### **Visit 3 (Day 14 ±3): Schirmer's Test Assessment**

- EDS (visual analog scale)
- BCVA (pre-and post-treatment)
- Slit lamp biomicroscopy (pre-and post-treatment)
- Administration of study drug/placebo
- Schirmer's Test (concurrent with treatment)
- Dispense study drug/placebo
- Concomitant Medications
- AE Query

### **Visit 4 (Day 28 ±4): Primary and Secondary Endpoint Assessment**

Visit 4 CAE® and Schirmer's Test Evaluation procedures are conducted on different days within the visit window. The Schirmer's Test Evaluation and all assessments should be performed after the CAE® visit assessments.

#### **Visit 4a**

##### **Pre- CAE® Procedures:**

- Urine pregnancy test (if applicable)
- EDS (visual analog scale)
- [REDACTED] Ocular Discomfort Scale
- BCVA
- Dispense study drug/placebo
- Concomitant Medications
- AE Query

##### **Pre-Treatment CAE® Evaluation**

- EDS (visual analog scale)
- [REDACTED] Ocular Discomfort Scale until threshold is met

### **ADMINISTRATION OF INVESTIGATIONAL DRUG/PLACEBO**

OC-01 (varenicline) Nasal Spray  
Clinical Trial Protocol # OPP-101  
Amendment #1

Sponsor: Oyster Point Pharma, Inc.

Treatment with Investigational drug/placebo will be administered upon a participant's reporting an Ocular Discomfort score  $\geq 3$  at two or more consecutive time points in at least one eye during CAE® exposure (participants with an Ocular Discomfort rating of 3 at time = 0 for an eye must report an Ocular Discomfort rating of 4 for two consecutive measurements for that eye (i.e. Threshold). Participants with an Ocular Discomfort rating of 4 at time = 0 for an eye must report an Ocular Discomfort rating of 4 for two additional consecutive measurements for that eye, not including time = 0 measurement) using the [REDACTED] Scale. Participants will resume symptom assessments (EDS and ODS) every 5 minutes starting 1 minute after the application ends.

**Post-Treatment CAE® Evaluation**

- EDS (visual analog scale)
- [REDACTED] Ocular Discomfort Scale

**Visit 4b (Minimum +3 Days after Visit 4a)**

**Schirmer's Test Evaluation:**

- EDS (visual analog scale) (post treatment)
- BCVA (pre and post treatment)
- Slit lamp biomicroscopy (pre and post treatment)
- Corneal fluorescein staining (post treatment)
- Intranasal examination (pre and post treatment)
- Administration of study drug/placebo
- Schirmer's Test (concurrent with treatment)
- Concomitant medications
- AE Query

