### 5.5 Withdrawal Criteria

If at any time during the study the Investigator determines that a subject's safety has been compromised, the subject may be withdrawn from treatment, but will be followed for safety for the duration of the study, unless they refuse to attend follow-up visits. Subjects will be asked to attend Visit 4b, Visit 5, Visit 6 and Visit 7 for endpoint and safety assessments.

Subjects may withdraw consent from the study at any time.

Sponsor and/or Investigator may discontinue any subject from study treatment for non-compliance or any valid medical reason during the course of the study (see [Section 8.6.2](#)).

OC-01 (varenicline) Nasal Spray  
Clinical Trial Protocol # OPP-101  
Amendment #1

Sponsor: Oyster Point Pharma, Inc.

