### 7.1.2 Dispensation Schedule

- At Visit 1, qualified subjects will be randomized and the first dose of study drug will be administered in office concurrent with Schirmer's test. The second daily administration will happen at home.
- At Visit 2, study drug/placebo will not be administered in office. Subject will self-administer study drug/placebo following their routine schedule.
- At Visit 3 the first daily dose of study drug will be administered in office concurrent with Schirmer's testing. The second daily administration will happen at home.
- At Visit 4a subjects will receive their first daily dose of study drug during CAE® exposure. The second daily administration will happen at home.
- At Visit 4b the first daily dose of study drug will be administered in office concurrent with Schirmer's testing.
- Between clinic visits, subjects will self-administer OC-01 (varenicline) Nasal Spray BID as a 50 µL dose in each nostril.

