### 8.6.3 Discontinued Subjects

Subjects may be discontinued from treatment, or from involvement in the study at any time prior to their completion of the study due to:

- Non-Fatal Adverse Event;
- Protocol Violations;
- Lost to Follow-up;
- Physician Decision;
- Subject Non-compliance;
- Death;
- Study Terminated by sponsor;
- Withdraw by Subject (e.g. withdrawal of consent); and
- Other

Note: In addition, any subject may be discontinued from treatment or from study involvement from any sound medical reason at the discretion of the investigator (after consultation with the Sponsor) or Sponsor.

Notification of a subject discontinuation and the reason for discontinuation will be made to [REDACTED] and/or Sponsor and will be clearly documented on the eCRF.

If the subject discontinues from treatment, they will be asked to be followed for safety for the duration of the study, unless they refuse to attend follow-up visits. Subjects will be asked to attend Visit 4b, Visit 5, Visit 6 and Visit 7 and have all scheduled assessments performed as per the Schedule of Visits and Measurements ([Appendix 1](#))

Discontinued subjects will not be replaced.

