6.2 Secondary Efficacy Endpoints

There are 11 secondary efficacy endpoints:

[figure not shown]
1. Mean change from Baseline in Eye Dryness Score (EDS) in the study eye at 5 minutes after threshold defined treatment administration in the Controlled Adverse Environment Chamber at Week 4 (Visit 4a)
2. Mean change from Baseline in Eye Dryness Score (EDS) in the study eye at Week 4 (Visit 4b)
3. Mean change from Baseline in Schirmer's Test Score (STS) in the study eye at Week 4 (Visit 4b)
4. Mean change from Baseline in Inferior Corneal Fluorescein Staining in the study eye at Week 4 (Visit 4b).
5. Mean change from Baseline in Eye Dryness Score (EDS) at Week 2 (Visit 3)
6. Mean change from Baseline in Eye Dryness Score (EDS) at Week 1 (Visit 2)
7. Mean change from Baseline in Nasal Corneal Fluorescein Staining in the study eye at Week 4 (Visit 4b)
8. Mean change from Baseline in Temporal Corneal Fluorescein Staining in the study eye at Week 4 (Visit 4b)
9. Mean change from Baseline in Central Corneal Fluorescein Staining in the study eye at Week 4 (Visit 4b)
10. Mean change from Baseline in Superior Corneal Fluorescein Staining in the study eye at Week 4 (Visit 4b)
11. Mean change from Baseline in Total Corneal Fluorescein Staining in the study eye at Week 4 (Visit 4b)

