10.1 Schirmer's Test

The Schirmer's Test with topical anesthetic will be performed to assess tear production at the Screening Visit (Visit 1). This first Schirmer's Test, which should be performed after corneal fluorescein staining, will be used as the baseline Schirmer's Test score. A second anesthetized Schirmer's Test with nasal stimulation using cotton swab will occur 10 minutes after the first anesthetized Schirmer's Test. Additional Schirmer's Tests with topical anesthetic will be assessed after the first treatment at Visit 1. At Week 2 (Visit 3), Week 4 (Visit 4b), the Schirmer's Tests will be performed concurrent with treatment.

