10.6 Corneal Fluorescein Staining

Corneal fluorescein staining will be performed and data will be collected at Screening (Visit 1), Week 4 (Visit 4b), and Early Termination (if necessary). Corneal fluorescein staining will be assessed for both the study and fellow eye. Staining will be graded using the National Eye Institute (NEI)/Industry Workshop Scale. Examiners will score each of five areas on the cornea of each eye: 1 – Central; 2 – Superior; 3 – Temporal; 4 – Nasal; 5 – Inferior. A standardized grading system of 0-3 will be used for each of the five areas. The corneal fluorescein staining score will be described by visit, treatment, study eye, and fellow eye with summary statistics. Specifically, scores will be presented by each of the five cornea areas and total scores for all corneal areas.

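### Does grading corneal staining only after the dose at Visit 4b, against a pre-dose baseline, spoil the Week-4 staining endpoints?

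*Protocol*

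**What the plan says.** **Visit 1.** SAP 10.1 says of the first Schirmer's test that it is the one "which should be performed after corneal fluorescein staining, will be used as the baseline" score. In Protocol 8.3.1, footnote 2, attached to the Schirmer's test done with dosing, reads "Procedure will occur after corneal fluorescein staining". Baseline staining is thus graded before any anaesthetic drop, strip, cotton swab or dose.

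**Visit 4b.** Protocol 7.1.2 states: "At Visit 4b the first daily dose of study drug will be administered in office concurrent with Schirmer's testing". The visit list in 8.3.1 then gives "Corneal fluorescein staining (post treatment" as the only staining entry. BCVA, slit lamp and intranasal examination are each listed both before and after treatment.

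**Endpoints.** SAP 6.2 item 4 is "Mean change from Baseline in Inferior Corneal Fluorescein Staining in the study eye at Week 4 (Visit 4b"); items 7 to 11 are the other four regions and the total. SAP 10.6 says "A standardized grading system of 0-3 will be used for each of the five areas" and names the visits, but not the timing within a visit. Protocol 6.1.2 marks the Week-4 EDS endpoint as taken after the Schirmer's test and puts no such mark on staining.

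**Subjects off treatment.** Protocol 5.5 says "Subjects will be asked to attend Visit 4b, Visit 5, Visit 6 and Visit 7 for endpoint and safety assessments", and 8.6.3 asks that they "have all scheduled assessments performed as per the Schedule of Visits and Measurements".

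**The concern.** A change score is easiest to read when both ends are measured under the same conditions. Here the baseline end is an undisturbed eye. The Week-4 end is an eye that has just had anaesthetic, a paper strip and a spray intended to raise tear production. Anaesthetic and strip are common to all arms, so their average effect largely cancels between arms, although it stays in each within-arm change. A same-day effect of the active spray does not cancel.

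A staining difference could therefore be read as healing of the corneal surface over four weeks when some or all of it arose in the preceding minutes. The label also fits awkwardly for a subject who attends Visit 4b after stopping treatment and has no dose that day.

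**Working it through.** **1. Is staining the odd one out at Visit 4b?** The measures, from Protocol 8.3.1 and SAP 10.1, with their role from Protocol 6.1 and 10.5.6:

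| Measure | Role | Baseline | Visit 4b |
|---|---|---|---|
| Schirmer's test | efficacy (primary) | no dose | during the dose |
| EDS | efficacy | before the dose | after the dose |
| Staining | efficacy | before the dose | after the dose |
| BCVA | safety | before (also after) | before and after |
| Slit lamp | safety | before (also after) | before and after |
| Intranasal exam | safety | before (also after) | before and after |

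Among the four examinations alone, 3 of 4 have a pre-treatment measure and staining does not. Among all six measures the split is 3 and 3, and it follows the role exactly: safety is before and after, efficacy is with or after the dose. Staining follows the pattern. The chamber EDS endpoint at Visit 4a, 5 minutes after dosing, does too.

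**2. What each timing estimates.** Let A be the same-day drug effect on staining and C the 28-day effect, each active minus placebo. If they add (an assumption):

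- post-dose grade: A + C
- pre-dose grade: C, provided nothing carries over from earlier twice-daily doses, which the documents do not show

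Either timing gives one equation for two unknowns. Separating A from C needs both grades; moving the single grade does not do it.

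**3. Size.** The plan gives no staining figure to reproduce. Its power figures (Protocol 10.4) concern other endpoints. With 250 per arm and two-sided 0.05 assumed, they do reproduce: 99.9996% for 15% versus 40% (stated as above 99%) and 99.93% for an EDS difference of 12 with SD 26 (stated as about 99%).

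For staining only illustrations are possible. The total runs to 5 × 3 = 15. Suppose a share f of an active arm shifts one grade on the day and no placebo subject does:

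| f | per region, f × 1 | total if all five regions shift, 5f |
|---|---|---|
| 5% | 0.05 | 0.25 |
| 10% | 0.10 | 0.50 |
| 20% | 0.20 | 1.00 |

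The sign could be either way.

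In SD units, the standard error of an arm difference is √(2/250) = 0.089, so the smallest significant difference is 1.96 × 0.0894 = 0.175 SD. With C = 0 and A = 0.1, 0.2 or 0.3 SD, the chance of a significant result is about 20%, 61% or 92%. Such a result would be a correct rejection for post-dose staining, not a false positive. Only the attribution to 28 days would be wrong.

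**4. Subjects off treatment.** If an assumed 5% or 10% of 250 attend Visit 4b undosed, that is 250 × 0.05 = 12.5 or 250 × 0.10 = 25 per arm. With A = 0.10 grade, the same-day part becomes 0.95 × 0.10 = 0.095 or 0.90 × 0.10 = 0.090, a change of 0.005 or 0.010 grade.

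**5. Endpoints touched.** Items 4, 7, 8, 9, 10 and 11 of SAP 6.2: 6 of 11, all from one examination. In the protocol it is 1 of 4 secondaries.

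**The case for a change.** The best case for a change is that the arms are expected to differ in wetting at the moment staining is graded. Protocol 10.4 recalls roughly 15% Schirmer's responders on placebo and 50% on each active dose in ONSET-1. The strip method in Appendix 2 asks the examiner to avoid provoking reflex tears when applying dye, and the synopsis reports EDS improvement within 5 minutes of dosing. A same-day effect on staining is therefore plausible. The remedy looks cheap: Visit 4b already has a pre-treatment block, and grading there would match baseline and would put fluorescein before the Schirmer's test at Visit 4b, as at Visit 1.

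The plausibility stands; the remedy is weaker than it looks. It removes the only post-dose staining grade, so a same-day effect would never be seen. It leaves staining as the only efficacy measure at Visit 4b taken before the dose. It changes the conditions of the primary Schirmer's test by an unknown amount and makes them differ from Visit 3, where no staining is listed. Subjects already assessed would carry the old timing.

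It is also fair that EDS is marked as post-Schirmer's in the endpoint list and staining is not. But the visit list states the staining timing and nothing readable in the SAP contradicts it, so a label would only repeat it. For subjects off treatment the protocol points to the Appendix 1 schedule, whose Visit 4b cells are not readable in the public copy, and SAP 9.5 and 12.2 are redacted. A gap cannot be asserted there.

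**Conclusion.** The order of procedures is as described, but no change to the plan follows. Post-dose grading is consistent with the other Visit 4b efficacy measures and suits the stated objective of effectiveness against placebo under twice-daily treatment. The randomised comparison and its type I error hold. Choosing a pre-dose grade instead is a choice of estimand with costs of its own, not a correction.

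The limit is on interpretation. A Week-4 staining difference should be reported as a difference in post-dose staining and not as a pure 28-day effect, and within-arm changes should be read knowing that anaesthetic and strip came first. An analyst reading the visit list would write it that way.

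The affected scope is one examination and 6 of 11 SAP secondaries, with the primary endpoint untouched. The true size is unknown; the shifts above rest on assumed shares of 5% to 20% and the dilution on assumed shares of 5% and 10%. The conclusion assumes that the unreadable schedule cells and redacted SAP sections do not contradict the Visit 4b list.

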**Visit 5 (Day 42  $\pm$  3): 6 Week Safety Assessment**

- Slit lamp biomicroscopy
- Intranasal examination
- Concomitant Medications
- AE Query

**Visit 6 (Day 168  $\pm$  7): 6 Month Safety Assessment**

- Slit lamp biomicroscopy
- Intranasal examination
- Concomitant Medications
- AE Query

**Visit 7 (Day 336  $\pm$  7): 12 Month Safety Assessment**

- Urine pregnancy test (if applicable)

OC-01 (varenicline) Nasal Spray  
Clinical Trial Protocol # OPP-101  
Amendment #1

Sponsor: Oyster Point Pharma, Inc.

- Slit lamp biomicroscopy
- Intranasal examination
- Concomitant Medications
- AE Query

## **8.4 Schedule of Visits, Measurements and Dosing**

### **8.4.1 Scheduled Visits**

Refer to [Appendix 1](#) for a schedule of visits and measurements.

### **8.4.2 Unscheduled Visits**

These visits may be performed in order to ensure subject safety. All procedures performed at an unscheduled visit will be recorded in the source documents and on the Unscheduled Visit eCRF pages. Any procedure indicated in the eCRF that is not performed should be indicated as “Not done.”

Evaluations that may be conducted at an Unscheduled Visit include:

- Slit-lamp Biomicroscopy;
- EDS
- BCVA
- Intranasal Examination;
- Corneal Fluorescein staining
- Urine Pregnancy Test (if applicable);
- Assessment of AEs;
- Assessment of concomitant medications and/or treatments; and
- Any other assessments needed in the judgment of the investigator.

## **8.5 Compliance with Protocol**

Subjects will be instructed on the proper use and storage of the study drug at Visits 1, 2, 3 and 4a, and provided with written instructions upon dispensation of their study drug at Visit 1..

## **8.6 Subject Disposition**

### **8.6.1 Treatment Completed Subjects**

A Treatment Completed Subject is one who has completed the first 4 weeks of study visits.

### **8.6.2 Safety Follow up Completed Subjects**

A Safety Follow up Completed Subjects is one who has completed all study visits up to Visit 7.

OC-01 (varenicline) Nasal Spray  
Clinical Trial Protocol # OPP-101  
Amendment #1

Sponsor: Oyster Point Pharma, Inc.

### 8.6.3 Discontinued Subjects

Subjects may be discontinued from treatment, or from involvement in the study at any time prior to their completion of the study due to:

- Non-Fatal Adverse Event;
- Protocol Violations;
- Lost to Follow-up;
- Physician Decision;
- Subject Non-compliance;
- Death;
- Study Terminated by sponsor;
- Withdraw by Subject (e.g. withdrawal of consent); and
- Other

Note: In addition, any subject may be discontinued from treatment or from study involvement from any sound medical reason at the discretion of the investigator (after consultation with the Sponsor) or Sponsor.

Notification of a subject discontinuation and the reason for discontinuation will be made to [REDACTED] and/or Sponsor and will be clearly documented on the eCRF.

If the subject discontinues from treatment, they will be asked to be followed for safety for the duration of the study, unless they refuse to attend follow-up visits. Subjects will be asked to attend Visit 4b, Visit 5, Visit 6 and Visit 7 and have all scheduled assessments performed as per the Schedule of Visits and Measurements ([Appendix 1](#))

Discontinued subjects will not be replaced.

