### 10.2 Analysis Populations

#### 10.2.1 Intention-To-Treat Population

The intent-to-treat (ITT) population will include all randomized subjects. Analyses using the ITT population will group subjects according to the treatment to which they were randomized.

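### Protocol 8.6.3 allows protocol violation or non-compliance to end study participation, not just treatment, which can leave ITT subjects without a Visit 4b outcome

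*Protocol*

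**What the plan says.** Protocol 8.6.3 opens with "Subjects may be discontinued from treatment, or from involvement in the study at any time prior to their completion of the study" and then a single list of reasons. The list includes "Protocol Violations" and "Subject Non-compliance" alongside death, loss to follow-up, withdrawal by the subject and termination by the sponsor. Nothing says which reasons end treatment only and which end participation. A note adds that "any subject may be discontinued from treatment or from study involvement from any sound medical reason".

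The follow-up rule in the same section is conditional: "If the subject discontinues from treatment, they will be asked to be followed for safety for the duration of the study". Those subjects are also asked to attend Visits 4b, 5, 6 and 7 with all scheduled assessments. No outcome collection is set for a subject discontinued from the study.

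Three other places bear on this:
- Protocol 5.5: "Sponsor and/or Investigator may discontinue any subject from study treatment for non-compliance or any valid medical reason during the course of the study". It mentions neither protocol violations nor removal from the study for non-compliance, and it refers the reader to 8.6.2, which defines subjects who completed safety follow-up.
- Protocol Section 4 asks those who terminate early during the application period for safety assessments only.
- SAP 9.8 gives nearly the same list, including protocol violation and non-compliance, as the case report form's reasons for discontinuing treatment.

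On the analysis side, Protocol 10.2.1 says "The intent-to-treat (ITT) population will include all randomized subjects". The SAP synopsis names this as the population for the primary analysis. Subjects with major deviations are excluded only from the per-protocol set (SAP 9.2.2).

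**The concern.** A site or the sponsor may, under the wording of 8.6.3, take a subject out of the study for a protocol violation or for non-compliance. That decision comes after randomisation. The subject remains in the ITT denominator, is not replaced, and has no planned Week 4 outcome.

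The Schirmer's score, which drives the primary endpoint, is the most exposed. SAP 10.1 places the Week 4 test at Visit 4b and names no Early Termination test. EDS and corneal staining may be collected at Early Termination (SAP 10.2 and 10.6), but those are not Week 4 values.

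The analysis does not need these removals, because the per-protocol set already excludes major deviators. What is at stake is outcome data that could have been collected at a scheduled visit. If the decision to remove depends on how the subject is faring on the assigned spray, the resulting missingness is not random.

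**Working it through.** **Inputs (Protocol 10.4).** About 750 randomised 1:1:1; about 250 per arm expected to have Visit 4 assessments; responder rates 15% on placebo and 40% on active; EDS difference 12 units, SD 26. Since 750/3 = 250, no loss is allowed for. Alpha is not in the readable text, so two-sided 0.05 is assumed.

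**1. The plan's own power figures.**
- Primary: pooled rate 0.275. SE under the null = sqrt(2 × 0.275 × 0.725/250) = 0.0399; under the alternative = sqrt((0.15 × 0.85 + 0.40 × 0.60)/250) = 0.0383. Power = Φ((0.25 − 1.96 × 0.0399)/0.0383) = Φ(4.48), above 99.99%. The protocol says greater than 99%.
- EDS: 12/(26 × sqrt(2/250)) = 5.16, so power = Φ(5.16 − 1.96) = Φ(3.20) = 99.9%. The protocol says approximately 99%.

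Both are reproduced.

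**2. Is power at risk?** With a fraction d of each arm lost, n = 250(1 − d):
- d = 20% (n = 200): primary 99.99%, EDS 99.6%.
- d = 30% (n = 175): primary 99.97%, EDS 99.1%.

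Power is not the issue.

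**3. Possible shift in the primary result.** The removal rate is not given; 3% to 5% is assumed, or about 8 to 12 of 250.
- Observed cases, with every removed active subject a non-responder and no removals on placebo: 100/250 = 40.0% becomes 100/242 = 41.3% to 100/238 = 42.0%, a shift of +1.3 to +2.0 points.
- The same in both arms: placebo becomes 37.5/242 = 15.5% to 37.5/238 = 15.8%. The difference becomes 62.5/242 = 25.8 to 62.5/238 = 26.3 points, a shift of +0.8 to +1.3.
- Missing counted as non-response, with removed subjects otherwise typical of their arm: difference = 25(1 − d), or 24.25 points at 3% and 23.75 at 5%, a shift of −0.75 to −1.25.

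**4. Extreme bound.** Every missing active subject is a non-responder and every missing placebo subject a responder. The difference is 0.40(1 − d) − [0.15(1 − d) + d] = 0.25 − 1.25d: 18.75 points at 5%, 12.5 at 10%, 6.25 at 15% and 0 at 20%. This limits what missing data could do; it is not a forecast.

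**5. The texts side by side.**
- Non-compliance: 8.6.3 allows exit from treatment or study; 5.5 mentions treatment only; SAP 9.8 lists it under treatment.
- Protocol violation: 8.6.3 allows either; 5.5 is silent; SAP 9.8 lists it under treatment.
- Visit 4b: 8.6.3 requests it after treatment discontinuation only; Section 4 asks early terminators for safety assessments only.

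**The case against.** The strongest reply is that this is loose wording with a natural benign reading. SAP 9.8 treats both reasons as treatment discontinuations, and 8.6.3 asks subjects who discontinue treatment to attend Visit 4b with all assessments. A site reading the documents together would keep the subject in follow-up. That makes loss of Visit 4b a possibility rather than a consequence, and this much stands. But SAP 9.8 describes a list for reporting. It does not withdraw the permission that 8.6.3 gives to sites.

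Several stronger readings are tempting and are not supported:
- **That 5.5 flatly contradicts 8.6.3.** Section 5.5 is permissive. Its Visit 4b sentence sits in the paragraph on subjects whose safety is compromised, not with the non-compliance sentence. On protocol violations it is silent, so there the documents have a gap rather than a conflict.
- **That subjects found ineligible after randomisation are removed.** No readable text says so; it would be an inference from the protocol-violation entry.
- **That sneezing on active spray would drive unequal removal.** The protocol's risk summary reports sneezing as the most common event in all treatment groups of the earlier study, gives no rates by arm, and does not link it to non-compliance.
- **That EDS suffers most.** EDS and staining have an Early Termination measurement; the Schirmer's test has none stated.

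It is also fair to say that the size rests on an assumed removal rate, and that the missing-data and analysis text (SAP 9.5, 12.1, 12.2, Appendix 2) is redacted.

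**Conclusion.** The point holds in a limited form. Section 8.6.3 permits, without requiring, study-level removal for protocol violation or non-compliance and plans no Visit 4b outcome for a subject so removed, while the ITT analysis keeps that subject. Sections 5.5 and 8.6.3 and SAP 9.8 do not describe the same rule.

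The likely effect on the primary endpoint is small: about 1 to 2 points, in a direction that depends on how missing values are handled, against a planned 25. This assumes 3% to 5% removal and the planning rates in Protocol 10.4. It would not by itself overturn a difference of that size, and power is unaffected. No bias in EDS was computed. Whether the planned missing-data methods would deal adequately with these subjects cannot be judged from the readable text, but no method recovers a Week 4 measurement that was never taken. The change is worth making because the loss is avoidable and prevention is cheap.

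**What to change.** Reconcile Protocol 5.5, 8.6.3 and Section 4 with SAP 9.8:
- Define discontinuation of treatment and withdrawal from the study separately.
- State that protocol violation or non-compliance alone does not end follow-up. These subjects are still asked to attend Visit 4b, with all endpoint assessments, and Visits 5 to 7, unless they withdraw consent, are lost to follow-up or die, or the study is terminated.
- Correct the cross-reference in 5.5 from 8.6.2 to 8.6.3.
- Record the two kinds of discontinuation separately on the eCRF disposition page, so that SAP 9.8 can report them apart.

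The grounds for stopping treatment and the medical-reason note in 8.6.3 are left as written; the change concerns data collection only. The cost is one amended paragraph, one eCRF page, and a few more subjects attending visits already scheduled. No sample-size or power figure changes.
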